4.5.2 Study exposure

Study exposure for patients entering the observation period for EP00-402 study is calculated as:

Study exposure (days) = Date of final visit – Date of baseline visit +1

Study exposure (days) will be converted to months as treatment exposure and will be summarized in a similar manner.

4.6 Analysis of primary endpoint

Patients in the safety set (SAF) are considered for analyzing the primary endpoint (and related endpoints).

4.6.1 Developing type II diabetes mellitus

Development of type II diabetes mellitus is the primary outcome measure, characterized by fulfilment of the following criteria:

- FPG \geq 126 mg/dl (7.0 mmol/l) during blood sampling and/or during OGTT
- 2-h plasma glucose \geq 200 mg/dl (11.1 mmol/l) during an OGTT
- Investigator documenting diagnosis of diabetes mellitus during OGTT

Accordingly, if lab values are elevated (both 2-hr plasma glucose and FPG) above the specified threshold for overt diabetes and investigator confirms with 'Yes' (question on OGTT page), consider the case for diabetes. But in case, 2-hr plasma glucose is elevated (overt) and FPG is normal/ impaired then investigator's response on diagnosis of diabetes will be considered only.

No inferential statistics is planned for this endpoint and results will only be interpreted in a descriptive manner.

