2.3 Endpoints

2.3.1 Primary Endpoint

The development of diabetes is the primary endpoint of the study and is evaluated on the basis of the carbohydrate metabolism (fasting plasma glucose (FPG) and oral glucose tolerance test (OGTT)).

Specifically of interest is, number and percentage of patients developing overt type II diabetes mellitus after the end of GH treatment, characterized by fulfilment of the following criteria:

- FPG \geq 126 mg/dl (7.0 mmol/l) during blood sampling and/or during OGTT
- 2-h plasma glucose \geq 200 mg/dl (11.1 mmol/l) during OGTT

Documented confirmation on diagnosis of diabetes mellitus by investigator during OGTT will also be considered to qualify incidence of elevated glucose values as development of overt type II diabetes mellitus.

Fasting plasma glucose as well as an OGTT will be measured at baseline (i.e. final visit of EP00-401), 6 months, 1, 5 and 10 years after the end of treatment.

Additional criteria – carbohydrate metabolism

Additionally, long term effect of growth hormone (GH) treatment on carbohydrate metabolism is also assessed by

- Change from baseline in FPG, baseline and 2hr plasma glucose (during an OGTT), fasting plasma insulin and glucose glycosylated hemoglobin (HbA_{1C}) at 6 months, 1, 5 and 10 years after the end of treatment.

- **Insulin resistance** will be estimated at baseline, 6 months, 1, 5 and 10 years after the end of treatment, using both the homeostasis model assessment (HOMA; Matthews et al. 1985) and quantitative insulin sensitivity check index (QUICKI; Katz et al. 2000):

$$\text{HOMA} = \frac{\text{fasting insulin } (\mu\text{U/ml}) \times \text{fasting glucose (mg/dl)}}{405.41^*}$$

*use constant 22.5 instead of 405.41 if glucose concentration is reported in mmol/L

$$\text{QUICKI} = \frac{1}{\log \text{fasting insulin } (\mu\text{U/ml}) + \log \text{fasting glucose (mg/dl)}}$$

Implausible insulin or glucose values will be excluded, i.e. Glucose values below 0.1 mmol/L and insulin values below 0.1 pmol/L will not be used for the calculation of HOMA and QUICKI.

Potential of GH-treatment induced insulin resistance will be captured through change from baseline in HOMA and QUICKI at 6 months, 1, 5 and 10 years after the end of treatment

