4.4.3 Concomitant medication

Information on administration of any medications, except investigational medicinal products, should have been reported in the appropriate section of the CRF, along with dose information, dates of administration and reason for use. Any diagnostic, therapeutic or surgical procedure should have also have been recorded, including the date, indication, descriptions of the procedure and clinical findings.

Concomitant medication will be coded according to WHO-DRL. For version and used update strategy for coding see coding guideline for this study. All documented concomitant medication data will be summarized separately by Anatomical Therapeutic Chemical (ATC) term (level 2) and preferred term, providing the number and % of patients to whom medication was administered. This summary will be prepared for the FAS analysis set.

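### A diabetes diagnosis made between assessments meets no counting rule for the primary endpoint if the patient's glucose is later controlled on treatment or no further OGTT is done

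*SAP*

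**What the plan says.** SAP 2.2 sets the primary objective as the effect of treatment on the development of diabetes over the 10 years after it ends. SAP 2.3.1 says that FPG and an OGTT "will be measured at baseline (i.e. final visit of EP00-401), 6 months, 1, 5 and 10 years after the end of treatment".

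SAP 4.6.1 lists three criteria: FPG at or above "126 mg/dl (7.0 mmol/l) during blood sampling and/or during OGTT"; 2-h glucose at or above "200 mg/dl (11.1 mmol/l) during an OGTT"; and "Investigator documenting diagnosis of diabetes mellitus during OGTT". Two sentences then say how to apply them. When both values are elevated, the text continues "investigator confirms with 'Yes' (question on OGTT page), consider the case for diabetes". When the 2-h value is elevated but FPG is normal or impaired, the investigator's response alone decides. SAP 2.3.1 gives that response a supporting role: "Documented confirmation on diagnosis of diabetes mellitus by investigator during OGTT will also be considered to qualify incidence of elevated glucose values".

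Two other sources could reveal a diagnosis made in ordinary care. On medication, SAP 4.4.3 states: "Information on administration of any medications, except investigational medicinal products, should have been reported in the appropriate section of the CRF", with dates and reason for use. SAP 4.7.1.3 provides for MedDRA-coded adverse events with start dates. Neither section is linked to the primary endpoint.

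**The concern.** Every input to the case rule is a blood sample or an entry on the OGTT page. Diabetes that arises between assessments may be diagnosed and treated by the patient's own physician. By the next visit glucose may be controlled, or the OGTT may not be repeated because the diagnosis is already known. Such a patient has clinically recognised diabetes and yet need not be a primary endpoint case.

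The study was set up to examine diabetogenic potential, and its primary result is a descriptive count. Losing recognised cases moves that count towards reassurance. One report could list diabetes as an adverse event in a patient whom the primary table does not count, and no rule in the SAP reconciles the two.

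**Working it through.** The SAP states no sample size, incidence or expected number of cases, so there is no figure to reproduce. The check compares the case rule with the schedule, the data sources and the analysis set.

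1. **Gaps between planned assessments (SAP 2.3.1).** Times are 0, 0.5, 1, 5 and 10 years. The gaps are 0.5 − 0 = 0.5, 1 − 0.5 = 0.5, 5 − 1 = 4 and 10 − 5 = 5 years. The two long gaps hold 4 + 5 = 9 of 10 years, or 90%.

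2. **Effect of termination (SAP 2.1, 4.1).** Patients were called in for a last visit, which is analysed under the 10 Years/Final label. If that visit falls at year T, with T between 5 and 10, the last gap is T − 5 years. The share of follow-up lying after year 1 is (T − 1)/T, from 4/5 = 80% at T = 5 to 9/10 = 90% at T = 10. For T between 1 and 5 there is a single gap of T − 1 years, and the share is below 80%.

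3. **A patient diagnosed in a gap, under SAP 4.6.1.**

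| Next assessment | Rule that applies | Case? |
|---|---|---|
| Both values elevated, investigator answers Yes | First applying sentence | Yes |
| 2-h value elevated, FPG normal or impaired, investigator answers Yes | Second applying sentence | Yes |
| Both values below threshold under treatment | Neither sentence; under 2.3.1 there is no elevated value to qualify | No, unless the third bullet is read as standing alone |
| No OGTT, FPG below threshold | None; no 2-h value and no OGTT page | No |
| No OGTT, FPG at or above threshold | First bullet is met, but neither sentence classifies the patient | Left open |
| No further visit, diabetes recorded only as an adverse event | None | No |

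4. **Analysis set.** SAP 4.6 analyses the primary endpoint in the safety population. SAP 2.6 admits a patient to that population with either a further visit date or an adverse event starting or worsening on or after baseline. The patient in the last row can therefore enter the set because of the diabetes event and still not be a case. SAP 4.8 imputes no missing safety values, so this patient is a non-case or missing.

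5. **Direction.** Let k be the true number of cases among N patients, with m of them missed. The reported proportion is (k − m)/N if the missed patients count as non-cases, or (k − m)/(N − m) if they drop out as missing. For m > 0 and k < N both are below k/N. The SAP gives none of k, m or N, so the size of the shortfall cannot be computed.

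**The case against.** **The rule is less restrictive than it first looks.** A reader might infer that any patient diagnosed between visits is lost. That is not so. A patient with an elevated 2-h value and a Yes from the investigator is counted even when FPG is normal. The loss is confined to patients controlled on both values and patients with no later OGTT. This stands.

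**Scheduled visits only.** A reader might also infer that unscheduled glucose samples are excluded. The SAP says so expressly only in the antibody paragraph of 2.3.2.1. The FPG criterion names no visit, and the CRF-visit rule in 4.1 concerns analyses by visit. The restriction is an inference, and the SAP should settle it.

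**The third bullet might stand alone.** Read in isolation, the investigator's diagnosis could be sufficient. SAP 2.3.1 and the two applying sentences in 4.6.1 point the other way, and a patient without an OGTT gains nothing from this reading.

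**The cases are still reported.** If recorded, they appear in the adverse event tables and listing, and any treatment appears in the medication summary. This is true and limits the harm to the report, but it does not correct the primary count. The absence of inferential testing does not help either, because the count is itself the result.

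**Laboratory ascertainment is a legitimate choice, and broadening it late has risks.** Adding every diabetes event would bring type 1 and other forms into a type II endpoint, and the definition would change after termination. Both points stand. They call for a restriction by type and for keeping the laboratory-based count visible.

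**The protocol may address this.** It is not at hand. The SAP, however, sets out its own case rule and mentions no further route.

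**Conclusion.** The concern holds in limited form. The case rule has no route for diabetes diagnosed between assessments when the patient is later controlled on both values or has no further OGTT, although the SAP describes data that could identify such patients. The bias is downward.

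Its size is unknown. A reader might take the 90% of planned follow-up that lies in the long gaps and, assuming a constant hazard, multiply it by a guessed fraction of onsets that are diagnosed and then controlled or untested. Fractions of 25% to 75% would give 0.90 × 0.25 = 22.5% to 0.90 × 0.75 = 67.5% of cases missed. The SAP supports neither assumption, and the 90% ignores earlier final visits, so that range should not be relied on.

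The conclusion rests on reading the investigator's answer as qualifying elevated glucose, as 2.3.1 words it. For patients with no later OGTT and no FPG at or above threshold, it holds on either reading.

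**What to change.** In SAP 2.3.1 and 4.6.1, before database lock:

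- Add a derived flag for post-baseline adverse events coded to type II diabetes or to diabetes of unspecified type. Show type 1 and other specified types separately.
- Add to the flag glucose-lowering medication started after baseline and recorded with diabetes as the reason for use.
- State that glucose values from unscheduled samples count towards the case rule.
- Report the primary table by route: laboratory- or OGTT-confirmed cases, additional cases identified from adverse events or medication, and the total.

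The cost is SAP wording, one derived variable and extra rows in a table, using data the CRF already provides for. The downside is that some added cases will lack laboratory confirmation or a clear diabetes type. The split by route makes this visible and leaves the laboratory-based count readable on its own.

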2.1 Study documents and general considerations

This document describes the procedures and conventions to be used in the final analyses with data of all patients who were included into study EP00-402.

The study is based on the

- study protocol V 1.0, dated 16 Mar 2007,
- Amendment no. 01, dated 12 Mar 2012 incorporated into protocol v 1.0 leading to protocol v 2.0, dated 12 Mar 2012,
- Amendment no. 02, dated 9 May 2012 incorporated into protocol v2.0 leading to protocol v3.0, dated 9 May 2012,
- Amendment no. 03, dated 6 Jun 2013 incorporated into protocol v3.0 leading to protocol v 4.0, dated 6 Jun 2013,
- Amendment no. 04, dated 14 July 2014 incorporated into protocol v4.0 leading to protocol v5.0, dated 14 July 2014.

This study was terminated by the sponsor [REDACTED] Following decision of [REDACTED] study termination all patients were called in for a last visit (documented on the final visit page of the case report form (CRF)).

Raw data listings, summary tables, graphs and statistical tests will be generated by means of the program SAS 9.3 or higher.

The following descriptive statistical parameters will be shown in summary tables

- Continuous variables: n (valid cases), n (missing data), mean, median, standard deviation (SD), min, max, quartiles
- Categorical variables: Count and percentage of category. Percentages are routinely based on the total category count excluding the missing category if not otherwise mentioned. Percentages showing a rate relative to the total number of patients in this group are given in special tables (e.g. Adverse Event (AE) tables). Footnotes will specify the percent basis.

For continuous variables, if not otherwise specified, mean, median and quartiles will be reported to one decimal place greater than the precision of data as collected. Standard deviation will be

presented in two decimal place greater than the data and minimum/ maximum values will be reported with the same precision, as they were collected. This rule is only valid if values are not converted for the summary.

Generally, percentages will be displayed in the format xx.d, i.e. one decimal place will be shown; if the calculated percentage is 100, no decimal is required (i.e. 100% and not 100.0%). If the count is zero no percentage needs to be shown.

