4.3 Protocol deviations

Number of protocol deviations as well as the number and percentage of patients with protocol deviations will be summarized overall and by protocol deviation category and classified reason for exclusion/protocol deviation for all enrolled patients. The summary of reported protocol deviations will be presented according to the following categories as agreed during data review meeting –

- Inclusion/exclusion criteria
- Withdrawal/ termination criteria met, but subject not discontinued
- Failure to perform key procedures
 - Lab values not taken
 - Study assessment not done
 - visit window (deviation from protocol specified visit schedule)
- GCP-related deviation

In addition all protocol deviations will be listed on a subject level.

According to the decisions made during the data review meeting prior to DBL, following patient will be excluded from the appropriate analyses sets with details as below:

Table 4-1 Summary of patients excluded from analysis set(s)

Patient	Analysis set excluded from	Reason for exclusion
[REDACTED]	SAF/ FAS	[REDACTED]

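### The primary endpoint case rule in SAP Section 4.6.1 gives no outcome for isolated high fasting glucose or a missing OGTT, and contradicts its own list of criteria

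*SAP*

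**What the plan says.** SAP Section 2.3.1 defines the primary endpoint as the number and percentage of patients developing overt type II diabetes after growth hormone treatment ends. It lists two glucose criteria with no connector between them: FPG of at least 126 mg/dl, which may be measured "during blood sampling and/or during OGTT", and 2-h glucose of at least 200 mg/dl in an OGTT. A separate sentence adds that the investigator's documented confirmation "will also be considered to qualify incidence of elevated glucose values as development of overt type II diabetes mellitus".

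Section 4.6.1 repeats the two glucose criteria, makes the investigator's diagnosis a third item, and again gives no connector. It then applies the list through two branches:

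- **Both values high.** The patient is a case "if lab values are elevated (both 2-hr plasma glucose and FPG) above the specified threshold for overt diabetes and investigator confirms with" 'Yes' on the OGTT page.
- **Only the 2-h value high.** Where "2-hr plasma glucose is elevated (overt) and FPG is normal/ impaired then" the investigator's "response on diagnosis of diabetes will be considered only".

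No further branch and no default is written.

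On the percentage, Section 4.6 names the safety set (SAF) as the population. Section 2.1 sets the general default: "Percentages are routinely based on the total category count excluding the missing category if not otherwise mentioned". It allows all-patient rates in special tables and leaves the base to footnotes. Section 4.3 has deviation categories for laboratory values not taken and for "Study assessment not done". Section 4.8 rules out imputation for safety parameters.

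**The concern.** The study exists to investigate diabetogenic potential, and no test is planned for this endpoint, so the count and percentage of cases are the whole primary result. A programmer working from Section 4.6.1 would have to invent an outcome for a patient with high FPG and a 2-h value below threshold. The same holds for high FPG from routine sampling when no OGTT was done. In that second situation the investigator's question may not be available either, because it sits on the OGTT page.

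The investigator's answer also changes role: supplementary in Section 2.3.1, a listed criterion in Section 4.6.1, a necessary condition in the first branch and the sole determinant in the second. Two competent programmers could report different primary counts from the same data, and both could claim to have followed the SAP.

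**Working it through.** The SAP states no figure to reproduce for this rule, so the check is an enumeration.

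**Inputs** (Sections 2.3.1 and 4.6.1): FPG high or not (126 mg/dl); 2-h glucose high or not (200 mg/dl); investigator 'Yes' or 'No'. With complete data there are 2 × 2 × 2 = 8 combinations, of which 6 have at least one elevated value.

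**Step 1: the branches against the Section 4.6.1 list.**

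| FPG | 2-h | Answer | Branches in 4.6.1 | List read as 'all three' | List read as 'any one' |
|---|---|---|---|---|---|
| high | high | Yes | case | case | case |
| high | high | No | non-case, by implication only | non-case | case |
| not high | high | Yes | case | **non-case** | case |
| not high | high | No | non-case | non-case | **case** |
| high | not high | Yes | no rule | non-case | case |
| high | not high | No | no rule | non-case | case |

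The branches give 2 cases, 2 non-cases and 2 combinations with no rule. If the implied non-case is not accepted, 3 of the 6 have no rule. The entries in bold are where an explicit branch outcome contradicts the list: row 3 rules out 'all three' and row 4 rules out 'any one'.

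**Step 2: missing values.** Allowing each input to be missing gives 3 × 3 × 3 = 27 combinations, of which the branches explicitly classify 3. High FPG with the 2-h value not high or missing accounts for 2 × 3 = 6 combinations (three possible answers each, counting blank); 0 of the 6 are classified. A blank answer has no stated outcome in either branch.

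**Step 3: filling the two unruled rows of Step 1.** Counting neither gives 2 case combinations. Letting the investigator decide gives 2 + 1 = 3. Counting both gives 2 + 2 = 4.

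**Step 4: Section 4.6.1 against Section 2.3.1.** Section 2.3.1 can be read in at least five ways. The two cases written in Section 4.6.1 are both high + 'Yes' and 2-h only + 'Yes'.

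| Reading of 2.3.1 | Case combinations | In the reading, not in 4.6.1 | In 4.6.1, not in the reading |
|---|---|---|---|
| Either value high | 6 | 4 | 0 |
| Both high, or any high + 'Yes' | 4 | 2 | 0 |
| Any high + 'Yes' | 3 | 1 | 0 |
| Both high | 2 | 1 | 1 |
| Both high + 'Yes' | 1 | 0 | 1 |

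The written set equals none of the five. Of the three fills in Step 3, only the 3-case fill matches a reading ('any high + Yes'). The 4-case fill has the same size as the second reading but a different membership.

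**Step 5: the branches as the whole rule.** Suppose everything not named is a non-case. Hold the 2-h value and the answer fixed and switch FPG between high and not high:

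- 2-h high, 'Yes': case both ways.
- 2-h high, 'No': non-case both ways.
- 2-h not high, 'Yes': non-case both ways.
- 2-h not high, 'No': non-case both ways.

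The outcome changes in 0 of 4 pairs. A case is then 2-h glucose of at least 200 mg/dl plus 'Yes', and the criterion listed first in both sections does nothing.

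**The case against.** The best defence is that Section 4.6.1 states a default (all three items met) and one exception (2-h value high alone), so anything else is a non-case. That makes the rule definite for complete data. But it is the rule tested in Step 5: it makes the FPG criterion idle, which cannot be squared with listing it first in both sections and accepting it from routine sampling. The default itself also has to be supplied by the reader.

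Other points carry some weight:

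- The analysis is descriptive, and the Section 4.6.2 listings show fasting glucose, 2-h glucose and the investigator's diagnosis by patient, so a reader could recount. That limits the harm, but the listings do not say who is a case.
- The five readings are constructions; the SAP states none of them, and the fourth ignores the confirmation sentence. They show ambiguity, not effect size.
- The grid of six omits 'Yes' with no elevated value, which 'any one' would also admit (7 of 8 overall). This does not alter the contradictions.
- FPG and OGTT are scheduled at the same visits, so FPG without an OGTT would be a missed assessment, and the Section 4.3 categories are general ones. That makes it less expected, but it still needs an outcome.
- The denominator is a secondary matter. The SAF is named and a footnote will show the base, so taken alone this would be only a missing detail.

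**Conclusion.** The concern holds and should be corrected before the analysis. Section 4.6.1 leaves isolated high FPG and high FPG without an OGTT unclassified, and its branches agree with neither an 'all' nor an 'any' reading of its own list. Section 2.3.1 does not repair this. Read as complete, the rule removes a stated primary criterion; read as incomplete, it allows two, three or four of the six elevated combinations to be cases. Either way, the primary count cannot be reproduced from the SAP without an unstated choice.

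The size is in combinations, not patients. The SAP gives neither the number of patients nor event counts, so the number affected and the direction of any miscount are not established. The tally of two non-cases assumes that both values high with 'No' is meant as a non-case.

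It is also not stated whether SAF patients who cannot be classified stay in the denominator of the primary percentage. For adverse events, by contrast, Section 4.7.1.3 names the SAF as divisor.

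**What to change.** Before database lock, the sponsor should:

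1. Reconcile Sections 2.3.1 and 4.6.1 into one algorithm that states the connector between the criteria and gives an outcome for every combination, including isolated high FPG, no OGTT, and an investigator answer of 'No' or blank.
2. Report two counts side by side: patients meeting the laboratory criteria, with the connector stated, and patients confirmed by the investigator.
3. State whether SAF patients who cannot be classified remain in the denominator, and footnote the base.

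This concerns classification for analysis only; the choice of diagnostic rule is the sponsor's.

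The cost is one rewritten paragraph, one derivation feeding two table rows, and one footnote. The inputs are already in the planned listings. The downside is that the reported count may move in either direction, and the laboratory-only count will include elevated values that the investigator did not confirm.

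### Section 4.6.1 needs an investigator 'Yes' in both glucose patterns it covers, so a patient above both thresholds with a 'No' or blank answer drops out of the primary diabetes count, and no glucose-only count is planned

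*SAP*

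**What the plan says.** SAP section 2.3.1 defines the primary endpoint as the "number and percentage of patients developing overt type II diabetes mellitus after the end of GH treatment, characterized by fulfilment of the following criteria". Two criteria follow: fasting plasma glucose (FPG) of at least 126 mg/dl, and 2-h glucose of at least 200 mg/dl in the OGTT. No 'and' or 'or' joins them. The section then adds that documented confirmation by the investigator "will also be considered to qualify incidence of elevated glucose values as development of overt type II diabetes mellitus".

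Section 4.6.1 repeats the two thresholds and adds a third bullet: "Investigator documenting diagnosis of diabetes mellitus during OGTT". It then gives the working rule in two branches:

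- Both values high: a case "if lab values are elevated (both 2-hr plasma glucose and FPG) above the specified threshold for overt diabetes and investigator confirms with 'Yes".
- 2-h value high, FPG not: "in case, 2-hr plasma glucose is elevated (overt) and FPG is normal/ impaired then investigator's response on diagnosis of diabetes will be considered only".

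Section 4.6.1 plans no inference for this endpoint. Section 4.8 imputes no missing values for safety parameters. Section 4.6.2 plans a patient-level OGTT listing with the fasting and 120-minute glucose values, whether diabetes was diagnosed, and comments. No table counts patients on the glucose criteria alone.

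**The concern.** Neither branch of the 4.6.1 rule lets glucose values make a case without the investigator's 'Yes'. A 'No', or a question nobody answered, therefore removes a patient whose values exceed both of the plan's own thresholds. The study was set up to examine the diabetogenic potential of growth hormone, and with no inference planned the number and percentage of cases is the primary result. In a safety endpoint, a condition that can only remove patients who meet the laboratory criteria should be visible in the summary table, not only in a listing.

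**Working it through.** The SAP states no sample size, expected rate or confirmation rate, so there is no figure to reproduce. The check enumerates the 4.6.1 rule for a single assessment.

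**Inputs.** Thresholds: FPG at least 126 mg/dl and 2-h glucose at least 200 mg/dl (2.3.1 and 4.6.1). Answer to the OGTT question: Yes, No or blank. Blanks are not turned into 'Yes' (4.8).

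**Enumeration.** Three glucose-positive patterns times three answers give 3 × 3 = 9 combinations.

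| Pattern | Yes | No | Blank | Meets 'either' | Meets 'both' |
|---|---|---|---|---|---|
| FPG high, 2-h high | case | not counted (implied) | not counted (implied) | yes | yes |
| FPG not high, 2-h high | case | not counted (explicit) | not counted (implied) | yes | no |
| FPG high, 2-h not high | no rule | no rule | no rule | yes | no |

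Two combinations are counted, four are not, and three have no rule: 2 + 4 + 3 = 9. The three without a rule are a separate gap and are not part of this point.

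**The decisive cells.** Both values high with 'No' or blank meets the glucose criteria under either joining word, yet is not counted. The missing 'and' or 'or' therefore does not explain the loss.

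**Size in those cells.** Let B be the number of patients with both values high and p the share of them answered 'Yes'. Then

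- count under 4.6.1 = p × B
- glucose count = B
- loss = (1 − p) × B, which is never negative

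With B = 5 assumed and no other glucose-positive patients, the expected count is:

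- p = 1.0: 5.0 (loss 0)
- p = 0.9: 4.5 (loss 0.5)
- p = 0.7: 3.5 (loss 1.5)
- p = 0.5: 2.5 (loss 2.5)

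**Direction outside those cells.** Assume 2 patients with both values high, 3 with the 2-h value only and 2 with FPG only. The 'either' count is 2 + 3 + 2 = 7 and the 'both' count is 2. If every answer is 'Yes', 4.6.1 counts 2 + 3 = 5. If half are, it counts 0.5 × 5 = 2.5. Both results lie below the 'either' count and above the 'both' count, so across all patterns the direction depends on a joining word that the SAP does not give.

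All cell counts and 'Yes' shares here are assumptions chosen to show the range.

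**The case against.** The other side has four arguments.

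1. *The sections may agree.* A reader might infer that 2.3.1 sets a purely laboratory endpoint and 4.6.1 contradicts it. The text does not support that firmly. Its sentence on confirmation speaks of qualifying elevated values as diabetes, which can fairly be read as a confirmation step, and 4.6.1 presents its rule as following from the criteria. This stands: 2.3.1 is ambiguous, and a flat contradiction is not shown.

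2. *The exclusions are partly inferred.* Only the branch with a high 2-h value alone makes the answer explicitly decisive. For both values high, 'No' fails the stated condition, but the outcome is not written out. Blanks are never mentioned. This stands as a description of the text, but it does not remove the problem: the rule requires 'Yes' and nothing supplies it when it is absent.

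3. *Confirmation guards against spurious single values.* This is a legitimate aim. Requiring it trades sensitivity for specificity, and the SAP does not show either choice to be an error. The answer is to show both counts.

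4. *Discordant patients are already traceable.* The listing in 4.6.2 puts the OGTT values beside the diagnosis. This stands in part: a careful reader could find these patients, but the reported number and percentage would not reveal them.

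**Conclusion.** The point holds for patients above both thresholds. On the natural reading of 4.6.1, a 'No' or blank keeps them out of the primary count, and for them that count can only equal the glucose count or fall below it. The size cannot be computed from the SAP and is zero if every such patient has a 'Yes'.

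A reader might go further and conclude that the whole primary count is biased low. The document does not support that. If both thresholds are required, 4.6.1 also admits patients with only the 2-h value high and a 'Yes', so its total can exceed a strict glucose count. The plan's description of a high 2-h value alone as overt favours the 'either' reading but does not settle it. Calling the difference bias would also presume that glucose values alone are the correct standard.

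This should be fixed because it concerns the case definition of the primary endpoint. It is not more serious than that: the endpoint is descriptive, the values are listed per patient, and the effect may be nil.

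**What to change.** Reconcile 2.3.1 and 4.6.1: state whether the investigator's confirmation is required, how 'No' and an unanswered question are handled, and which count is the headline. Then report two rows for the primary endpoint:

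- **(a) Laboratory-defined:** patients meeting the glucose criteria at any post-baseline assessment, whatever the investigator's answer. Show 'either threshold' and 'both thresholds' separately, because 2.3.1 does not fix the joining word and two programmers could otherwise produce different counts.
- **(b) Investigator-confirmed:** cases with a 'Yes'. Among the patients in row (a), show the number of blank answers separately from the number of 'No' answers.

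In the OGTT listing of 4.6.2, flag each patient whose glucose values and investigator answer disagree. No new listing is needed.

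The cost is SAP wording, a few table lines and one flag, all from data already collected. The downside is that row (a) may include unconfirmed single values. The flag makes these visible, and row (b) keeps the confirmed count beside it.
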